8.2. Subject Exclusion Criteria

Subjects who meet any of the following criteria will be excluded from the study:

1. Hospital discharge for sickle cell crisis or other vaso-occlusive event within the 4 days prior to randomization (Day 1).
2. Subjects participating in a chronic/prophylactic RBC transfusion program (i.e., regularly scheduled RBC transfusions); any transfusions within 21 days of screening or baseline Hb measurements.
3. Subjects with HbF >25% at screening.
4. Subjects with known active hepatitis A, hepatitis B, or hepatitis C, with active or acute event of malaria, or who are known to be positive for human immunodeficiency virus (HIV).

5. For female subjects of childbearing potential, a positive serum human chorionic gonadotropin (hCG) test (screening) or a positive urine hCG test at randomization (Day 1).
6. Significant kidney disease as indicated by, for example, estimated glomerular filtration rate (eGFR) <45 mL/min as calculated by the equation from the Modification of Diet in Renal Disease (MDRD) Study using creatinine, age, sex, and ethnicity (modified MDRD formula).
7. Alanine aminotransferase (ALT) or aspartate aminotransferase (AST) >3× the upper limit of normal.
8. Body mass index (BMI) <17.0 kg/m² or >35 kg/m²; or total body weight <45 kg.
9. Current or history of malignancies (solid tumors and hematological malignancies), unless the subject has been free of the disease (including completion of any active or adjuvant treatment for prior malignancy) for ≥5 years. However, subjects with the following history of/concurrent conditions are allowed if, in the opinion of the investigator, the condition has been adequately diagnosed and is determined to be clinically in remission, and the subject's participation in the study would not represent a safety concern:
 - a. Basal or squamous cell carcinoma of the skin
 - b. Carcinoma in situ of the cervix
 - c. Carcinoma in situ of the breast
 - d. Incidental histologic finding of prostate cancer (T1a or T1b using the tumor, nodes, metastasis clinical staging system)
10. History of a clinically significant allergic reaction or hypersensitivity, as judged by the investigator, to any drug or any component of the study drug formulations used in the study (see the IB).
11. History of unstable or deteriorating cardiac or pulmonary disease within 6 months before signing the ICF, including but not limited to the following:
 - a. Unstable angina pectoris or myocardial infarction or elective coronary intervention
 - b. Congestive heart failure requiring hospitalization
 - c. Uncontrolled clinically significant arrhythmias
12. Any condition affecting drug absorption, such as major surgery involving the stomach or small intestine (prior cholecystectomy is acceptable).
13. On ECG testing at ICF signing and/or randomization (Day 1), a QTcF >450 ms in men and >470 ms in women on 2 or more of the triplicate ECGs, or the presence of clinically significant ECG abnormalities as determined by the investigator.
14. Major surgery within 8 weeks or minor surgery within 2 weeks of randomization (Day 1).

15. Stroke requiring medical intervention within 24 weeks prior to randomization (Day 1).
16. Subjects taking DOACs (apixaban, dabigatran, rivaroxaban, edoxaban, or ticagrelor) or taking warfarin, unless they stopped the treatment at least 28 days prior to randomization (Day 1); low molecular weight heparins are allowed in the peri-operative period; aspirin use (<100 mg per day) is allowed before and during the study.
17. Poorly controlled diabetes mellitus in the opinion of the investigator, for example
 - 1) Hb A1c >9.0% within 12 weeks prior to randomization (in the medical history);
 - 2) short-term hyperglycemia leading to hyperosmolar or ketoacidotic crisis; and/or
 - 3) history of diabetic cardiovascular complications.
18. Subject has received chronic systemic glucocorticoids within 12 weeks prior to randomization (≥ 5 mg/day prednisone or equivalent). Physiologic replacement therapy for adrenal insufficiency is allowed.
19. Any clinically significant bacterial, fungal, parasitic, or viral infection requiring antibiotic therapy should delay screening/randomization (Day 1) until the course of antibiotic therapy has been completed. This includes, but is not limited to, long-term tuberculosis treatment.
20. Participated in another clinical study of an investigational agent (or medical device) within 30 days or 5 half-lives of date of informed consent, whichever is longer, or is currently participating in another study of an investigational agent (or medical device).
21. Prior exposure to IMR-687.
22. History of crizanlizumab (Adakveo[®]) or voxelotor (Oxbryta[®]) use within 6 months prior to signing the ICF or anticipated need for such agents during the study.
23. Consumption/use of the following drugs or other substances within the specified time periods before randomization or plans to consume/use at any time during the study. If there is any question as to whether a substance is permitted, please review the product labeling (if applicable) and consult the medical monitor and/or sponsor.
 - a. Phosphodiesterase type 5 (PDE5) inhibitors (including but not limited to sildenafil, tadalafil, and vardenafil) within 7 days prior to randomization (Day 1) or plans to use during the study.
 - b. Grapefruit, grapefruit juice, grapefruit products, or herbal supplements with CYP altering abilities within 1 week prior to randomization (Day 1) or plans to consume during the study.
 - c. CYP3A-sensitive substrates, including the opioids fentanyl and alfentanil, or moderate to strong CYP3A inhibitors or inducers within 28 days prior to randomization (Day 1) or plans to use during the study.
 - d. Any drugs or substances known to be substrates or inhibitors of P-gp or BCRP within 28 days prior to randomization (Day 1) or plans to use during the study.

24. Receipt of erythropoietin, luspatercept (Reblozyl®), or other erythropoiesis-stimulating or erythroid maturation agent within 6 months prior to signing the ICF or anticipated need for such agents during the study.
25. Prior gene therapy.
26. Any significant medical condition, laboratory abnormality, or psychiatric illness that would prevent the subject from participating in the study, including the presence of laboratory abnormalities that may place the subject at unacceptable risk if he/she were to participate in the study.
27. Other prior or ongoing medical condition, physical findings, or laboratory abnormality that, in the investigator's opinion, could adversely affect the safety of the subject, make it unlikely that the course of treatment or follow-up would be completed, or impair the assessment of study results (e.g., a history of drug or alcohol abuse within the past 1 year, as judged by the investigator).

8.3. Screen Failures

Any subject who consents to participate in the study but is not randomized will be considered a screen failure. Demographic data, eligibility criteria, primary reason for screen failure, and any SAEs (if applicable) will be recorded and reported in the subject's electronic case report form (eCRF) for subjects who are considered screen failures.

If a subject is considered a screen failure, then he/she may be rescreened once with sponsor approval.

8.4. Guidelines for Withdrawal of Subjects from Study Participation

Subjects will be informed that they withdraw from participation in the study at any time and for any reason, without prejudice to further medical care.

The investigator may also remove a subject from the study at their discretion if, in the investigator's opinion, it is not in the best interest of the subject to continue in the study.

If a subject must be withdrawn from study participation, the medical monitor should be informed and consulted regarding possible appropriate assessments to be completed in advance of study withdrawal. In case of withdrawal from the study, every effort will be made to complete both the early termination (ET) visit assessments and the EOS visit assessments, if possible. If a subject does not complete the ET assessments, every effort should be made to obtain the EOS assessments; in this case, the ET and EOS visits will coincide. If a final visit is not feasible, every effort to collect follow-up medical records will be attempted.

In the case of subjects who are lost to follow-up, the study site must attempt to contact the subject by phone, making at least 3 documented attempts, each at least 1 week apart. Additionally, a registered letter must have been sent with a copy on file. The study site should only deem the subject as lost to follow-up no less than 30 days following the first documented phone call attempt, unless circumstances preclude this (e.g., phone service has been discontinued or there is other evidence that contact is not feasible).

If the subject withdraws from the study, the specific circumstances surrounding the withdrawal must be recorded in the subject's eCRF.

Refer to Section [8.6](#) for details on subject replacement.

Justifiable reasons to discontinue a subject from treatment (Section [8.5](#)) and/or from the study may include, but are not limited to the following:

- The subject was erroneously included in the study (i.e., did not meet eligibility criteria)
- The subject experiences an SAE assessed as possibly or probably related to study drug
- The subject is unable to comply with the requirements of the protocol
- The subject participates in another investigational study
- The subject withdraws consent to participate in the study
- A subject for whom the blind is intentionally or accidentally broken

8.5. Guidelines for Study Drug Dose Withholding or Discontinuation

In consultation with the medical monitor, the investigator may decide to withhold or discontinue study drug dosing in cases where tolerability or safety concerns emerge. [Table 2](#) provides recommended guidelines for these decisions.

If a study drug dosing is withheld due to an AE (Section [12](#)), subjects who continue on the study will have all assessments (except study drug administration) performed as per protocol.

If study drug dosing is discontinued for any reason, the specific circumstances surrounding the discontinuation must be recorded in the subject's eCRF. Any subject who discontinues study drug dosing must also be withdrawn from the study; however, all appropriate safety assessments and follow-up should be completed prior to withdrawal (Section [8.4](#)).

Table 2: Safety Guidelines for Study Drug Dose Reduction, Withholding, or Discontinuation

Dose Reduction	
Event	Recommended Action
A Grade 2 or higher TEAE that, in the opinion of the investigator, is both study drug related and that makes continued dosing at the current dose level inadvisable due to safety concern or lack of tolerability.	
Study drug may be reduced by 1 tablet for up to 14 continuous days.
 
If, in the opinion of the investigator, a longer dose reduction is clinically needed, the medical monitor should be contacted.
 
If, in the opinion of the investigator, the severity of the Grade ≥ 2 TEAE has reduced to Grade ≤ 1, the subject may resume study drug at the original dose. If the TEAE recurs after re-introduction of the original dose, the subject should be withdrawn from the study.

Dose Interruption (Hold)	
Event	Recommended Action
A Grade 3 or higher TEAE that, in the opinion of the investigator, is both study drug related and that makes continued dosing at the current dose level inadvisable due to safety concern or lack of tolerability.	
Study drug should be held for up to 7 continuous days until reduction in severity of the TEAE to Grade ≤ 2, then resumed at the original dose.
 
If, in the opinion of the investigator, dosing should be resumed at a lower dose, the medical monitor should be contacted.
 
If, in the opinion of the investigator, a longer dose hold is clinically needed, the medical monitor should be contacted or the subject should be withdrawn from the study.

Positive test results for COVID-19 and/or similar illness (asymptomatic and symptomatic).	Study drug should be held until 7 days after subject tests negative. Please consult with the medical monitor if there are any questions regarding when to resume study drug.

Abbreviations: COVID-19 = coronavirus disease 2019; TEAE = treatment-emergent adverse event.

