12. SAFETY MONITORING AND REPORTING

12.1.1. Adverse Event and Serious Adverse Event Collection

12.1.1.1. Time Period Adverse Event Collection

All AEs and SAEs, related and unrelated, will be recorded from the signing of informed consent through the EOS safety follow-up visit. Events that occur following administration of study drug will be considered TEAEs.

All SAEs will be recorded and reported to the sponsor or sponsor's designee within 24 hours, as indicated in Section 12.1.2.3. The investigator will also submit any updated SAE data to the sponsor within 24 hours of the data being available.

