11.4 Intent-to-Treat Analysis Set

The intent-to-treat (ITT) analysis set will include all randomized subjects. The ITT set will be used as the primary analysis set to summarize efficacy, PD, and clinical outcome parameters. Subjects will be analyzed according to their randomized treatment assignment.

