13.5.2.1 Derivation of Annualized Rate of VOCs

As described in Protocol Inclusion Criterion 3, a VOC is defined as a documented episode of acute painful crisis (for which there was not an explanation other than VOC) that involves moderate to severe pain lasting for at least 2 hours and at least one of the following:

- Use of escalated analgesia (including healthcare professional-instructed use of an analgesic prescription)
- A hospital, emergency department, or clinic visit and/or healthcare telephone consultation at the time of occurrence
- Diagnosis of acute chest syndrome (ACS) (defined as an acute illness characterized by fever and/or respiratory symptoms, accompanied by a new pulmonary infiltrate on a chest X-ray), hepatic sequestration, or splenic sequestration, or priapism (in males)

VOCs collected during the study are assumed to meet these criteria as well.

VOC information, including start and end date/time, primary setting for treatment (hospitalization/ emergency department, etc.), and treatments are collected on the "VOC" CRF page.

Annualized rate of VOCs is calculated as Total number of VOCs / ([Date of last dose of study drug– date of first dose of study drug + 1]/365.25).

Date of last dose of study drug is collected from the "End of Treatment" CRF page. If that date is not available (which is expected for some of the subjects in the IA), the data cut-off date will be used.

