13.5.2.3 Missing Value Consideration for the Primary Efficacy Analysis

The value of the primary endpoint, annualized rate of VOCs, will be non-missing by definition. However, subjects included in the ITT analysis may not all complete the 52-week treatment period. In the context of this endpoint, the unobserved VOC events after treatment discontinuation will be considered missing values. This calculation accounts for early treatment discontinuation by extrapolating the VOC rate annualized to one year. The primary analysis assumes the unobserved rate of VOC will be the same for the observed rate for the same subject.

Missing data will not be imputed for primary endpoint analysis methods. Data imputation strategies will be employed for sensitivity analysis.

Understanding the reasons why data are missing is important to correctly interpret and handle the observed data. If the missing data mechanism is independent of missing outcome values, conditional on earlier observed outcome variables and/or covariates, the outcome values are missing at random (MAR). If the probability of missingness depends on an outside variable not in the model or is related to unobserved outcome values at the time of dropout and possibly afterward then the values are missing not at random (MNAR).

Table 8 summarizes the classification with the potential reasons. The missing data pattern will be summarized and the impact of these missing values will be explored in the sensitivity analysis below.

Table 8 Classification of Missing Data Pattern

| Missing Data Pattern | Reason for Treatment Discontinuation |
|------------------------------|---|
| MNAR (Missing Not at Random) | 
Due to efficacy/safety related reasons:
 
 • Adverse Event • Death • Lack of Efficacy • Lost to Follow-up • Non-Compliance with Study Protocol • Non-Compliance with Study Drug • Physician Decision • Study Terminated by Sponsor • Subject Participation in Another Investigational Study • Trial Site Terminated by Sponsor • Withdrawal of Consent • Other (efficacy/safety related) |
| MAR (Missing at Random) | 
Due to non-efficacy/non-safety related reasons:
 
 • Pregnancy • Study Blind Intentionally or Accidentally Broken • Subject Erroneously Included in Study (i.e. did not meet eligibility criteria) • COVID-19 • Other (not efficacy/safety related) |

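### Stopping study drug ends study participation, so the ITT primary analysis is in effect a while-on-treatment VOC rate

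*Protocol*

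**What the plan says.** Protocol 8.5: "Any subject who discontinues study drug dosing must also be withdrawn from the study". The same section treats a temporary hold differently: "subjects who continue on the study will have all assessments (except study drug administration) performed as per protocol". After withdrawal, Protocol 8.4 says that "every effort will be made to complete both the early termination (ET) visit assessments and the EOS visit assessments, if possible", with medical records as a fallback. Under Protocol 12.1.1.1, adverse events "will be recorded from the signing of informed consent through the EOS safety follow-up visit". Nothing provides for VOC follow-up to Week 52 off drug.

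SAP 11.4: "The ITT set will be used as the primary analysis set to summarize efficacy, PD, and clinical outcome parameters". SAP 13.5.2.1: "Annualized rate of VOCs is calculated as Total number of VOCs / ([Date of last dose of study drug", and the formula goes on to subtract the first-dose date, add one day and divide by 365.25. SAP 13.5.2.3 accepts that "the unobserved VOC events after treatment discontinuation will be considered missing values" and adds: "The primary analysis assumes the unobserved rate of VOC will be the same for the observed rate for the same subject". The primary analysis uses no imputation.

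SAP 13.5.2.4 plans completer and non-completer analyses, a jump-to-reference (J2R) analysis, two tipping-point analyses and multiple imputation. It also plans a negative binomial model whose offset is treatment exposure.

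**The concern.** All randomised subjects are in the analysis, but their outcomes after stopping drug are not. Carrying the on-drug rate forward is hard to defend for an active drug once it is stopped. SAP Table 8 itself classes 12 of its 17 listed discontinuation reasons as missing not at random, including adverse event, lack of efficacy and physician decision.

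Two things are at stake. If VOC rates drift back towards placebo after stopping, the estimate overstates the effect of assigning subjects to the drug. Separately, a rate annualised from a few weeks is usually zero and occasionally very large, and a rank test treats the zeros as good outcomes. If more subjects stop early on active drug than on placebo, that alone can favour the drug.

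**Working it through.** **1. The plan's own power figures reproduce.** Inputs from SAP 8.1.2 and Appendix 7: two-sided alpha 0.05, SD 2.7, means 5.034 and 3. I used noncentral t power with each sample size multiplied by 3/π, the Wilcoxon efficiency for normal data.

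| Scenario | Stated | At 2.034 | At 2.0 |
|---|---|---|---|
| 49 v 31, no dropout | 0.880 | 0.886 | 0.876 |
| 37 v 24, 25% dropout | 0.776 | 0.788 | 0.775 |

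The 25% scenario deletes dropouts. The ITT analysis keeps all 49 and 31 with extrapolated rates, so that scenario does not describe the planned analysis.

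**2. Size of the overstatement.** Assumptions that are not in the documents: active-arm subjects who stop revert at once to the placebo rate, and dropouts spend a fraction f of the year on drug. With dropout d, the true difference is 2.034 × (1 − d(1 − f)). For d = 25% and f = 0.25, this is 2.034 × 0.8125 = 1.65.

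| d | f = 0.25 | f = 0.50 | f = 0.75 |
|---|---|---|---|
| 10% | 1.88 | 1.93 | 1.98 |
| 25% | 1.65 | 1.78 | 1.91 |
| 35% | 1.50 | 1.68 | 1.86 |

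At the SAP's 25%, the planned 2.034 is too large by a factor of 2.034/1.91 = 1.06 to 2.034/1.65 = 1.23.

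**3. Short exposure.** For a subject who stops at Week 4, the chance of no VOC is exp(−3 × 4/52) = 79% at 3 per year and exp(−5 × 4/52) = 68% at 5 per year. Such a subject is ranked at 0 per year. A single VOC in those 28 days becomes 365.25/28 = 13 per year.

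**4. Simulation.** Gamma-Poisson counts with a 52-week SD of 2.7, 49 v 31 subjects, an unstratified Wilcoxon test at two-sided 0.05, and 10,000 trials per setting. The table gives the chance of a significant result favouring drug when both arms have 5 VOCs per year (nominal 2.5%).

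| Dropout (placebo/active), timing | Extrapolated rate | Full follow-up |
|---|---|---|
| 10%/35%, Weeks 1–12 | 6.5% | 2.5% |
| 10%/35%, Weeks 1–24 | 4.1% | 2.3% |
| 10%/35%, Weeks 1–52 | 3.5% | 2.5% |
| 25%/25%, Weeks 1–52 | 2.5% | 2.4% |

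Repeat runs of the first setting gave 6.7% to about 7%. In that setting the mean rates agree (4.99 and 5.00), but the median is 4.0 on active and 5.0 on placebo. The zeros cause the shift.

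**5. J2R as printed (SAP 13.5.2.4, item 4.1).** The bracket puts the observed VOC count over 365.25 as well. Take 2 VOCs in 100 days and a placebo rate of 5 per year. The remaining days by the SAP rule are 364 − 99 + 1 = 266.
- Printed: (2 + 5 × 266)/365.25 = 3.65 per year.
- Intended: 2 + 5 × 266/365.25 = 5.64 per year.

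Step 2 of the multiple imputation (item 4.3) is printed with the same bracket.

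**6. Numerator and denominator.** The count in SAP 13.5.2.1 has no stated end, while the time stops at last dose. A VOC recorded between last dose and the end of study visit could count without its time at risk.

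**The case against.** The strongest reply has five parts.

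- **The scenario is already planned for.** J2R gives dropouts the placebo completers' rate, and the delta tipping point and multiple imputation probe further. That deserves credit. But these analyses model the data rather than collect it, and the J2R formula is faulty as printed.
- **ITT in SAP 11.4 defines who is analysed, not an estimand.** This stands. The estimate is overstated only relative to the effect of assignment whatever happens to treatment, and the documents do not claim that estimand. They should say which one is meant.
- **The direction is not fixed.** This also stands. With equal dropout there is no excess of false positives. With 25% in both arms in Weeks 1–12 and a real effect, extrapolation loses power (75% against 82% with full follow-up).
- **Not everything is lost, and not everything is recoverable.** Early termination and end of study visits, records and adverse event reports will catch some events, so a reader should not infer that post-discontinuation VOCs are never observed. Deaths, losses to follow-up and consent withdrawals stay missing under any amendment.
- **It is late.** Randomisation ended in August 2021 (SAP 8.1.1) and the SAP is dated 1 March 2022, so all subjects were past nominal Week 24. The early stops, which distort most, had already happened.

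A reader might also infer that power falls from the stated 88% to about 78%. The documents do not support this. The 88% is the no-dropout figure, and SAP Table 1 already gives 78% for 25% dropout. In the count simulation with 25% dropout spread over the year, power was about 89% by extrapolation and 88% with full follow-up.

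**Conclusion.** The point holds as one of bias and estimand, not of power. The protocol ends VOC follow-up at drug discontinuation, and the primary analysis fills the gap with each subject's own on-drug rate. At 25% dropout the true difference would be about 1.65 to 1.9 VOCs per year, against a planned 2.03. A false-positive excess (about 6% to 7% against 2.5%) appears when early dropout is much heavier on active drug, shrinks as dropout comes later, and vanishes when dropout is equal. Reversion to the placebo rate, dropout timing and the split between arms are all assumptions. The change is worth making, but its benefit is now partial.

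**What to change.** 1. Amend Protocol 8.5 so that subjects who stop study drug without withdrawing consent stay in the study, with VOCs and concomitant medication collected at the remaining visits or by telephone to Week 52. Section 8.4 already distinguishes leaving treatment from leaving the study. No rule on when drug is stopped needs to change.
2. Reconcile the other passages that tie an event to study withdrawal: Table 2 in 8.5, 9.6.2 (prohibited medication), 10.4 (unblinding) and 12.1.2.5 (pregnancy).
3. Add to the SAP an ITT analysis of all observed VOCs over time in study, and define numerator and denominator over the same period.
4. Correct the J2R formula, and the same bracket in the multiple imputation step.
5. For subjects already withdrawn, describe the primary analysis as on-treatment and report the corrected J2R result beside it.

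Cost: items 3 to 5 are SAP edits. Items 1 and 2 need a protocol amendment with regulatory and IRB/IEC approval (Protocol 15.1.1) at about 70 sites, although the visits are already scheduled. The amendment helps only subjects who stop after it takes effect. With last randomisation in August 2021, Week 52 falls at about August 2022. Follow-up will then differ between earlier and later discontinuations, and the report should say so.
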